6.3.3.4 Mandatory dose modifications and recommended clinical management of serious skin reactions

Withhold trametinib for intolerable or severe skin toxicity. Resume trametinib at reduced doses in subjects with improvement or recovery from skin toxicity within 3 weeks. In cases of Stevens-Johnson syndrome and toxic epidermal necrolysis, permanently discontinue dabrafenib, trametinib and PDR001 and institute supportive care as per institutional guidelines.

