6.3.1 General dose modification instructions for PDR001 or placebo

No dose reductions are allowed for PDR001. Dose interruption for PDR001/placebo includes delaying or withholding the treatment for any reason as well as an interruption of treatment during an infusion. Subjects with adverse events suspected to be related to PDR001 or placebo including those of potential immune-mediated etiology (irAE) (see definition in [Section 6.3](#)) must be permanently discontinued from PDR001 or placebo if (1) the AE doesn't recover to ≤ Grade 1 or baseline within 12 weeks and/or (2) the dose of steroids (for the management of irAE) remains > 10 mg/day prednisone or equivalent for >12 weeks.

The 12 week timeframe will begin from the time the irAE reaches a grade that leads to PDR001/placebo interruption.

Subjects who discontinue the study for a study related adverse event or an abnormal laboratory value must be followed as described in [Section 7](#).

6.3.2 General dose modification instructions for dabrafenib and trametinib:

[figure not shown]
If treatment related toxicities occur that are specific to combination treatment of dabrafenib and trametinib, then both treatments should be simultaneously dose reduced, interrupted or discontinued with the exceptions shown below:

Exception where dose modification is necessary for **only dabrafenib**:

- Uveitis ([Table 6-25](#))

Exception where dose modifications are necessary for **only trametinib**:

- Retinal vein occlusions (RVO) ([Table 6-25](#)) and retinal pigment epithelial detachment (RPED) ([Table 6-26](#))
- Left ventricular ejection fraction (LVEF) reduction ([Table 6-22](#))

If a subject’s dose of dabrafenib and trametinib has been reduced per the dose modification instructions, re-escalation of the subject’s dose is recommended provided the following criteria are met:

- a period of 4 weeks of treatment has passed since restarting dosing at the lower dose level and there is no recurrence of the AE
- the subject is deriving clinical benefit

For dabrafenib and/or trametinib related adverse events: if following an interruption of dabrafenib and trametinib, an AE doesn’t recover to ≤ Grade 1 or baseline within 4 weeks, dabrafenib and trametinib must be discontinued.

6.3.3 Dose modification and management guideline for adverse events common to PDR001, dabrafenib and trametinib

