6.3.3.3 Mandatory dose modifications and recommended clinical management guidelines for skin rash

Guidelines for dose modification and management of skin rash considered to be related to study treatment by the investigator are provided in [Table 6-11](#).

Table 6-11 Mandatory dose modifications and recommended clinical management guidelines for rash

Rash Events (NCI-CTCAE v4.03)		
Grade	Recommended adverse event management guidelines	Mandatory dose modification requirements
Grade 1: Rash covering < 10% body surface area	
 Initiate prophylactic and symptomatic treatment measures. Consider use of topical corticosteroids or urea containing creams in combination with oral antipruritics or moderate strength topical steroid (hydrocortisone 2.5% cream or fluticasone propionate 0.5% cream) Reassess after 2 weeks 	
 Continue PDR001/placebo, dabrafenib and trametinib at the same dose.
Grade 2: 10-30% of body surface area	
 If tolerable, as per Grade 1 	
 If tolerable, continue PDR001/placebo, dabrafenib and trametinib at the same dose.

Rash Events (NCI-CTCAE v4.03)		
Grade	Recommended adverse event management guidelines	Mandatory dose modification requirements
	
 If intolerable, initiate systemic steroids (0.5 to 1 mg/kg/day prednisone or equivalents) If symptoms persist or recur consider skin biopsy. 	
 If intolerable: 
1st occurrence
 
 Interrupt PDR001/placebo, dabrafenib and trametinib until ≤ Grade 1, and then reinstate PDR001 treatment (after appropriate steroid tapering) and reduce dabrafenib and trametinib to the next dose level per Table 6-7. Re-escalation of the subject's dose is recommended if criteria in Section 6.3.2 are met. AE resolution to ≤ Grade 1 or baseline must occur within a period of 12 weeks since a Grade 3 event has been identified, otherwise PDR001 must be permanently discontinued.

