Grade 3: More than 30% of body surface area	
 Obtain a skin biopsy and dermatology consult. Initiate therapy with high dose steroids (1 to 2 mg/kg/d prednisone or equivalents) 	
1st occurrence
 
 Interrupt PDR001/placebo, dabrafenib and trametinib until ≤ Grade 1, and then reinstate PDR001 treatment (after appropriate steroid tapering), and reduce dabrafenib and trametinib to the next dose level per Table 6-7. Re-escalation of the subject's dose is recommended if criteria in Section 6.3.2 are met. AE resolution to ≤ Grade 1 or baseline must occur within a period of 12 weeks since a grade 3 event has been identified, otherwise PDR001 must be permanently discontinued. 
2nd occurrence
 
 Permanently discontinue PDR001/placebo. Interrupt dabrafenib and trametinib until ≤ Grade 1 or baseline. Once recovered, reduce dabrafenib and trametinib to the next dose level per Table 6-7. Re-escalation of the subject's dose is recommended if criteria in Section 6.3.2 are met. 
3rd occurrence
 
 Interrupt dabrafenib and trametinib until ≤ Grade 1 or baseline. Once recovered, reduce dabrafenib and trametinib to the next dose level per Table 6-7. Re-escalation of the

Rash Events (NCI-CTCAE v4.03)		
Grade	Recommended adverse event management guidelines	Mandatory dose modification requirements
		subject's dose is recommended if criteria in Section 6.3.2 are met.
		4th occurrence
		
 Permanently discontinue PDR001/placebo, dabrafenib and trametinib.
Grade 4: Life-threatening	
 Same as Grade 3 	
 Permanently discontinue PDR001/placebo, dabrafenib and trametinib.

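### Two mandatory skin rules overlap for intolerable Grade 2 and Grade 3 rash and restart trametinib on different criteria

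*Protocol*

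**What the plan says.** Three places in the protocol bear on the same kind of event.

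- **Section 6.3.3.4 (serious skin reactions, headed mandatory).** Its trigger, action and restart rule are "Withhold trametinib for intolerable or severe skin toxicity. Resume trametinib at reduced doses in subjects with improvement or recovery from skin toxicity within 3 weeks". The other two drugs appear only in the next sentence: "In cases of Stevens-Johnson syndrome and toxic epidermal necrolysis, permanently discontinue dabrafenib, trametinib and PDR001".
- **Section 6.3.3.3, Table 6-11 (rash, headed mandatory).** For a first Grade 3 rash: "Interrupt PDR001/placebo, dabrafenib and trametinib until ≤ Grade 1, and then reinstate PDR001 treatment (after appropriate steroid tapering), and reduce dabrafenib and trametinib". The row for intolerable Grade 2 rash gives the same instruction at first occurrence. Both rows carry a 12-week limit whose only stated consequence is loss of PDR001; the Grade 3 row reads "must occur within a period of 12 weeks since a grade 3 event has been identified, otherwise PDR001 must be permanently discontinued".
- **Section 6.3.2 (general rules for dabrafenib and trametinib).** For toxicities specific to that combination, "then both treatments should be simultaneously dose reduced, interrupted or discontinued with the exceptions shown below". Skin toxicity is not among the exceptions. For events related to either drug, both must be stopped if the event has not returned to Grade 1 or below, or to baseline, within 4 weeks of interruption.

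Table 6-8 lists skin rash and serious skin reaction on separate rows, pointing to Sections 6.3.3.3 and 6.3.3.4 respectively. It marks PDR001, dabrafenib and trametinib on both rows as drugs that may need modification.

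**The concern.** The trigger in Section 6.3.3.4 is not confined to Stevens-Johnson syndrome or toxic epidermal necrolysis, which have their own sentence. An intolerable Grade 2 rash meets both triggers as worded, and a Grade 3 rash is severe skin toxicity on any ordinary reading. Such a patient falls under two mandatory rules with no order of precedence.

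Section 2.6 names skin rash as a toxicity that PDR001 may share with dabrafenib and trametinib. In Table 3-1, tolerability is measured by dose interruptions, reductions and dose intensity, and Section 4.3 keeps safety data collection open after the final PFS analysis. If sites follow different sections, the same rash produces different exposure records, and monitors have no single standard for judging a deviation. The first matter at stake is patient safety; the second is how the tolerability summaries can be interpreted.

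**Working it through.** No arithmetic applies, so the check sets the texts side by side.

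**1. What each text directs for an intolerable Grade 2 or a Grade 3 rash, first occurrence**

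| | Section 6.3.3.4 | Table 6-11 | Section 6.3.2 |
|---|---|---|---|
| Drugs named | trametinib | all three | dabrafenib and trametinib together |
| Restart or recovery criterion | improvement or recovery | Grade 1 or below | Grade 1 or below, or baseline |
| Limit, trametinib | 3 weeks, no stated consequence | none | 4 weeks, then stop |
| Limit, dabrafenib | none | none | 4 weeks, then stop |
| Limit, PDR001 | none | 12 weeks, then stop | not covered |

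**2. Courses of a first Grade 3 rash, and what happens to trametinib**

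- *Grade 1 or below by week 2.* Section 6.3.3.4 resumes trametinib at a reduced dose. Table 6-11 does the same, one level down. The texts agree.
- *Down to Grade 2 in week 2, then unchanged.* Section 6.3.3.4 resumes trametinib, because the rash has improved within 3 weeks. Table 6-11 keeps it interrupted, because the rash is above Grade 1. The instructions are opposite, for the same drug on the same day.
- *Grade 1 first reached between weeks 3 and 4.* Section 6.3.3.4 gives no instruction once its window has passed. Table 6-11 restarts at a lower dose. Section 6.3.2 has not yet reached its limit.
- *Still above Grade 1 after 4 weeks of interruption.* If the event is related to dabrafenib or trametinib, Section 6.3.2 stops both. Table 6-11 gives no limit for either. Section 6.3.3.4 is silent, or has already restarted trametinib if the rash had improved.

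**3. Which drugs are held.** Outside the two named syndromes, Section 6.3.3.4 mentions trametinib and does not mention dabrafenib or PDR001/placebo. Table 6-11 holds all three at first occurrence. From the second Grade 3 occurrence it stops PDR001/placebo permanently and interrupts the other two.

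**4. How far the restart mismatch extends.** For the second and third Grade 3 occurrences, Table 6-11 still requires Grade 1 or below, or baseline, before dabrafenib and trametinib restart. The difference in restart criterion is therefore not confined to the first occurrence.

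**5. Precedence.** Neither Section 6.3.3.3, Section 6.3.3.4, Section 6.3.2 nor Table 6-8 says which rule governs when both apply.

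**The case against.** The case for leaving the text alone has real force in several places.

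*A reader might infer a conflict of 3 weeks against 12 weeks.* The documents do not support that. The 12 weeks decide only whether PDR001 is permanently stopped, and the 3 weeks concern only resuming trametinib. Limits on different drugs can coexist.

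*A reader might infer that Section 6.3.3.4 orders trametinib to be held alone.* It does not say so. Where the protocol means another drug to go on, it says so, as for dabrafenib in Table 6-13 (pneumonitis) and Table 6-25 (visual changes). Section 6.3.3.4 has no such words, so what it leaves on the other drugs is silence.

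*A reader might infer that no handling can satisfy both rules.* That is too strong. A site that holds all three drugs, sees Grade 1 or below within 3 weeks and restarts trametinib one level lower has met both texts.

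*The scopes differ.* Table 6-8 sends rash and serious skin reaction to different sections, and the Amendment 2 log describes Section 6.3.3.4 as added for serious skin reactions. That suggests an intended division, but the operative trigger does not draw it: intolerable rash fits the words of both sections.

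*Section 6.3.2 is worded for the doublet.* Its joint-modification rule covers toxicities specific to dabrafenib plus trametinib. Rash sits in Section 6.3.3, which warns that triplet guidance may differ. This stands, so Section 6.3.2 supports the need to reconcile but does not by itself prove a contradiction. Likewise 3 against 4 weeks is a misalignment, since Section 6.3.3.4 states no consequence after week 3.

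None of this removes the opposite trametinib instructions for a rash that improves but stays above Grade 1.

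**Conclusion.** The point holds in a limited form. Two mandatory rules overlap for intolerable Grade 2 and Grade 3 rash and contradict each other on when trametinib restarts. The contradiction bites when the rash improves within 3 weeks but remains above Grade 1. Around it lie two lesser defects: silence on dabrafenib and PDR001/placebo in Section 6.3.3.4, and a 3-week window with no consequence that does not align with the 4-week limit in Section 6.3.2.

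The number of patients affected cannot be derived. Section 1.2.2.2.3 puts rash among events in more than 20% of patients on dabrafenib plus trametinib, but that is all grades; at Grade 3 or 4 it lists only hypertension and pyrexia at 5% or more. The 88 Part 3 patients still on treatment at Amendment 7 are everyone on treatment, not those with rash. No figure supports a stated effect on dose intensity.

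The conclusion assumes that Grade 3 rash counts as severe skin toxicity. For intolerable Grade 2 rash no such assumption is needed. It is no judgement on which rule is clinically right. The text should be corrected because the conflict concerns patient management and the correction is cheap.

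**What to change.** Reconcile Section 6.3.3.4, Table 6-11 and Section 6.3.2 in one of two ways:

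- For each skin event covered by more than one passage, state one set of drugs to interrupt, one restart criterion and one time limit per drug, with the consequence when the limit passes.
- Or state explicitly that Section 6.3.3.4 applies only to events that Table 6-11 does not cover, and name those events. Even then, give the 3-week window a stated consequence and say how it relates to the 4-week limit.

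Check that the two skin rows of Table 6-8 still match. The sponsor's clinical team decides the content.

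The cost is wording in one short section and, where needed, one table and a cross-reference, plus a letter to sites. No added data, visits or patients are needed.

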6.3.3.5 Mandatory dose modifications and recommended clinical management guidelines for nephritis

[figure not shown]
Guidelines for does modification and management of nephritis considered to be related to study treatment by the investigator are provided in [Table 6-12](#).

Table 6-12 Mandatory dose modifications and recommended clinical management guidelines for renal function alterations

NCI-CTCAE v4.03		
Grade	Recommended adverse event management guidelines	Mandatory dose modification requirements
Grade 1 (Creatinine > ULN to ≤ 1.5× ULN)	
 Monitor creatinine weekly If creatinine return to baseline resume routine creatinine monitoring per protocol Promote hydration and cessation of nephrotoxic drugs. 	
 Continue PDR001/placebo, dabrafenib and trametinib at the same dose.
Grade 2 (Creatinine > 1.5× to ≤ 3× ULN)	
 Monitor creatinine every 2 to 3 days Initiate 0.5 to 1 mg/kg/day prednisone equivalents If worsening or no improvement: increase to 1 to 2 mg/kg/day prednisone equivalents Consult with specialist and consider renal biopsy Promote hydration and cessation of nephrotoxic drugs. 	
1st occurrence
 
 Interrupt PDR001/placebo, dabrafenib and trametinib until ≤ Grade 1 or baseline and then reinstate PDR001 treatment and dabrafenib and trametinib at the same dose. AE resolution to ≤ Grade 1 must occur within a period of 12 weeks since Grade 2 event has been identified. Otherwise, PDR001/placebo must be permanently discontinued. 
2nd occurrence:

NCI-CTCAE v4.03		
Grade	Recommended adverse event management guidelines	Mandatory dose modification requirements
		
 Permanently discontinue PDR001/placebo. Interrupt dabrafenib and trametinib until \leq Grade 1 or baseline. Once recovered, reduce dabrafenib and trametinib to the next dose level per Table 6-7. Re-escalation of the subject's dose is recommended if criteria in Section 6.3.2 are met. 
3rd occurrence:
 
 Interrupt dabrafenib and trametinib until \leq Grade 1 or baseline. Once recovered, reduce dabrafenib and trametinib to the next dose level per Table 6-7. Re-escalation of the subject's dose is recommended if criteria in Section 6.3.2 are met. 
4th occurrence
 
 Permanently discontinue dabrafenib and trametinib.
Grade 3 (Creatinine > 3.0 to < 6 \times ULN)	
 Monitor creatinine every 1 to 2 days. Start 1 to 2 mg/kg/day prednisone equivalents Consult with nephrologist. Promote hydration and cessation of nephrotoxic drugs. 	
1st occurrence:
 
 Interrupt PDR001/placebo, dabrafenib and trametinib until \leq Grade 1 or baseline and then reinstate PDR001 then reduce dabrafenib and trametinib to the next lower dose per Table 6-7. Re-escalation of the subject's dose is recommended if criteria in Section 6.3.2 are met. AE resolution to \leq Grade 1 or baseline must occur within a period of 12 weeks since the Grade 3 event has been identified, otherwise PDR001/placebo must be permanently discontinued 
2nd occurrence:
 
 Permanently discontinue PDR001/placebo. Interrupt dabrafenib and trametinib until \leq Grade 1 or baseline and then reduce dabrafenib and trametinib to the next lower dose per Table 6-7. Re-escalation of the subject's dose is recommended if criteria in Section 6.3.2 are met. 
3rd occurrence:

NCI-CTCAE v4.03		
Grade	Recommended adverse event management guidelines	Mandatory dose modification requirements
Grade 4: Creatinine > 6× ULN	
 Monitor creatinine daily. Initiate steroids with 1 to 2 mg/kg/day prednisone equivalents Consult with specialist and recommend renal biopsy. Promote hydration and cessation of nephrotoxic drugs. 	
 Interrupt dabrafenib and trametinib until ≤ Grade 1 or baseline and then reduce dabrafenib and trametinib to the next lower dose per Table 6-7. Re-escalation of the subject's dose is recommended if criteria in Section 6.3.2 are met. 
4th occurrence:
 
 Permanently discontinue dabrafenib and trametinib. Permanently discontinue PDR001/placebo, dabrafenib and trametinib.

6.3.3.6 Mandatory dose modifications and recommended clinical management guidelines for pneumonitis

[figure not shown]
Guidelines for dose modification and management of pneumonitis considered to be related to study treatment by the investigator are provided in [Table 6-13](#).

Table 6-13 Mandatory dose modifications and recommended clinical management guidelines for pneumonitis

Pneumonitis (NCI-CTCAE v4.03)		
Grade	Recommended adverse event management guidelines	Mandatory dose modification requirements
Grade 1: Radiographic changes only- Asymptomatic	
 CT scan (high-resolution with lung windows) recommended, with serial imaging to monitor for resolution or progression- re-image at least every 3 weeks Monitor for symptoms every 2-3 days - Clinical evaluation and laboratory work-up for infection Monitoring of oxygenation via pulse oximetry recommended Consultation of pulmonologist recommended. 	
 Continue dabrafenib and trametinib at the same dose. Interrupt PDR001/placebo, until recovery to baseline. 
 Once recovered, reinitiate PDR001/placebo at the same schedule. If worsens, treat as Grade 2 or 3-4. AE resolution to ≤ Grade 1 or baseline must occur within a period of 12 weeks since Grade 1 event has been identified, otherwise PDR001 /placebo must be permanently discontinued
Grade 2: Symptomatic-medical intervention indicated; limits instrumental ADLs	
 CT scan (high-resolution with lung windows) 	
1st occurrence:
 
 Interrupt PDR001/placebo, and trametinib until recovery to ≤ Grade

Pneumonitis (NCI-CTCAE v4.03)

Grade	Recommended adverse event management guidelines	Mandatory dose modification requirements
	
 • Monitor symptoms daily, consider hospitalization • Clinical evaluation and laboratory work up for infection • Consult pulmonologist • Pulmonary function tests - if normal at baseline, repeat every 8 weeks • Bronchoscopy with biopsy and/or BAL recommended • Symptomatic therapy including corticosteroids if clinically indicated (systemic corticosteroids at a dose of 1 to 2 mg/kg/day prednisone or equivalent as clinically indicated). 	
1 or baseline. Dabrafenib may continue at the same dose.
 
 • Once recovered, reinstate PDR001/placebo at same schedule and reduce trametinib to the next lower dose per Table 6-7. Re-escalation of the subject's dose is recommended if criteria in Section 6.3.2 are met. • If no recovery to \leq Grade 1 within 4 weeks, permanently discontinue trametinib. Dabrafenib may continue. • AE resolution to \leq Grade 1 or baseline must occur within a period of 12 weeks since Grade 2 event has been identified, otherwise PDR001/placebo must be permanently discontinued. • If worsens treat as Grade 3 or 4. 
2nd occurrence:
 
 • Permanently discontinue PDR001/placebo. • Interruption of trametinib until recovery to Grade 1 or baseline. Dabrafenib may continue at the same dose.

Pneumonitis (NCI-CTCAE v4.03)		
Grade	Recommended adverse event management guidelines	Mandatory dose modification requirements
Grade 3: Severe symptoms; limits self-care ADLs; oxygen indicated	
 CT scan (high-resolution with lung windows) Clinical evaluation and laboratory work-up for infection Consult pulmonologist Pulmonary function tests-if < normal, repeat every 8 weeks until \geq normal Bronchoscopy with biopsy and/or BAL if possible Treat with intravenous steroids (methylprednisolone 125 mg) as indicated. When symptoms improve to \leq Grade 1, a high dose oral steroid (prednisone 1 to 2 mg/kg once per day or dexamethasone 4 mg every 4 hours). If IV steroids followed by high dose oral steroids does not reduce initial symptoms within 48 to 72 hours, consider non-corticosteroid immunosuppressive medication (e.g., infliximab, cyclophosphamide, IVIG or mycophenolate mofetil). 	
 Permanently discontinue PDR001/placebo. Interrupt trametinib until recovery to Grade \leq1 or baseline. Dabrafenib may continue. 
 Once recovered, trametinib may be restarted at the next lower dose per Table 6-7. Re-escalation of the subject's dose is recommended if criteria in Section 6.3.2 are met. If no recovery to Grade \leq 1 or baseline within 4 weeks, permanently discontinue trametinib. Dabrafenib may continue.
Grade 4: Life- threatening respiratory compromise	
 Same as Grade 3 	
 Same as Grade 3

6.3.3.7 Mandatory dose modifications and recommended clinical management guidelines for encephalitis

[figure not shown]
Guidelines for dose modification and management of encephalitis considered to be related to study treatment by the investigator are provided in [Table 6-14](#).

Table 6-14 Mandatory dose modifications and recommended clinical management guidelines for encephalitis

Encephalitis		
Grade	Recommended adverse event management guidelines	Mandatory dose modification requirements
Grade 1: Asymptomatic or mild symptoms		
 Continue PDR001/placebo, dabrafenib and trametinib at the same dose.

Encephalitis		
Grade	Recommended adverse event management guidelines	Mandatory dose modification requirements
Grade 2: New onset of moderate symptoms, limiting instrumental ADL	
 Consider consulting with neurologist Treat with 0.5 to 1 mg/kg/day prednisone equivalents 	
1st occurrence:
 
 Interrupt PDR001/placebo, until recovery to \leq Grade 1 or baseline. 
 Once recovered, restart PDR001/placebo at the same dose. AE resolution to \leq Grade 1 or baseline must occur within a period of 12 weeks since Grade 2 event has been identified, otherwise PDR001/placebo must be permanently discontinued. 
If it worsens, treat as Grade 3 – 4.
 
2nd occurrence:
 
 Permanently discontinue PDR001/placebo. Continue dabrafenib and trametinib at the same dose. 
3rd occurrence:
 
 Permanently discontinue dabrafenib and trametinib.
Grade 3 or 4: New onset of severe symptoms, limiting self-care ADL, life-threatening	
 Recommend consultation with neurologist. Treat with 1 to 2 mg/kg/day prednisone equivalents. 	
1st occurrence:
 
 Permanently discontinue PDR001/placebo. Interrupt dabrafenib and trametinib until recovery to \leq Grade 1 or baseline. Once recovered, reduce dabrafenib and trametinib at the next dose level per Table 6-7. Re-escalation of the subject's dose is recommended if criteria in Section 6.3.2 are met. 
2nd occurrence:
 
 Permanently discontinue dabrafenib and trametinib.

6.3.3.8 Mandatory dose modifications and recommended clinical management guidelines for endocrine events

Guidelines for does modification and management of endocrine events considered to be related to study treatment by the investigator are provided in [Table 6-15](#).

Table 6-15 Mandatory dose modifications and recommended clinical management guidelines for endocrine events

Endocrine events (NCI-CTCAE v4.03)		
Grade	Recommended adverse event management guidelines	Mandatory dose modification requirements
Asymptomatic, intervention not indicated (hyperthyroidism or hypothyroidism)	
 • If TSH <0.5x LLN, or TSH >2x ULN, or consistently out of range in 2 subsequent measurements, include free T4 at subsequent cycles as clinically indicated • Consider endocrinologist consult • If hypophysitis is considered, pituitary gland imaging should be considered (MRIs with gadolinium and selective cuts of the pituitary can show enlargement or heterogeneity and confirm the diagnosis) • Repeat labs in 1 to 3 weeks/MRI in 1 month if laboratory abnormalities persist but normal lab/pituitary scan 	
 • Continue PDR001/placebo, dabrafenib and trametinib at the same dose.
Symptomatic endocrinopathy (e.g., hypophysitis, adrenal insufficiency, hypothyroidism, hyperthyroidism)	
 • Consider Endocrinology consultation • Rule out infection and sepsis with appropriate cultures and imaging • Treat with an initial dose of methylprednisolone 1 to 2 mg/kg intravenously followed by oral prednisone 1 to 2 mg/kg per day. • Replacement of appropriate hormones may be required as the steroid dose is tapered • Hypophysitis with clinically significant adrenal insufficiency and hypotension, dehydration, and electrolyte abnormalities (such as hyponatremia and hyperkalemia) constitutes adrenal crisis • Consider hospitalization and intravenous methylprednisolone should be initiated. 	
1st occurrence:
 
 • Interrupt PDR001/placebo, until symptomatic recovery to mild or no symptoms. 
 • Once recovered, restart PDR001/placebo. • AE resolution to mild or no symptoms must occur within a period of 12 weeks since symptomatic endocrinopathy event has been identified, otherwise PDR001/placebo must be permanently discontinued. 
2nd occurrence:
 
 • Permanently discontinue PDR001/placebo and may continue dabrafenib and trametinib at the same dose.

6.3.3.9 Mandatory dose modifications and recommended clinical management guidelines for hand-foot reaction (palmar-plantar erythrodysesthesia)

[figure not shown]
In general, management of hand-foot skin reactions include:

- Prevention/prophylaxis: promote sunscreen use and avoidance of unnecessary sun exposure, use alcohol-free emollient creams, topical steroids and antibiotics as needed.
- Pruritic lesions: cool compresses and oral antihistamines
- Fissuring lesions: Monsel’s solution, silver nitrate or zinc oxide cream
- Desquamation: thick emollients and mild soap
- Paronychia: antiseptic bath, local potent corticosteroids, antibiotics, surgery as needed
- Infected lesions: topical or systemic antibiotics
- Measures for PPES should include:
 - Lifestyle modification: avoidance of hot water, traumatic activity, constrictive footwear, or excessive friction on the skin and the use of thick cotton socks and gloves, and shoes with padded insoles
 - Symptomatic treatments: apply moisturizing creams frequently, topical keratolytics (e.g., urea 20-40% cream, salicylic acid 6%, tazarotene 0.1% cream, fluorouracil 5% cream), clobetasol propionate 0.05% ointment for erythematous areas, topical lidocaine 2%, and / or systemic pain medication such as nonsteroidal anti-inflammatory drugs, codeine, and pregabalin for pain.

Guidelines for dose modification for hand foot skin reaction considered to be related to study treatment by the investigator are provided in [Table 6-16](#).

Table 6-16 Mandatory dose modifications and recommended clinical management guidelines for hand foot skin reaction (palmar-plantar erythrodysesthesia)

Hand foot skin reaction		
Grade	Recommended adverse event management guidelines	Mandatory dose modification requirements
Grade 1: Numbness, dysesthesia, paresthesia, tingling, painless swelling, erythema or discomfort of the hands or feet which does not disrupt the subject’s normal activities	
 • Recommend topical therapy for symptomatic relief. 	
 • Continue PDR001/placebo, dabrafenib and trametinib at the same dose.

Hand foot skin reaction		
Grade	Recommended adverse event management guidelines	Mandatory dose modification requirements
Grade 2: Painful erythema and swelling of the hands or feet and/or discomfort affecting the subject's normal activities	
 Recommend topical therapy for symptomatic relief 	
 Continue treatment and if no improvement within 7 days, see below. No improvement within 7 days or 2nd or 3rd occurrence: 
 Interrupt PDR001/placebo, dabrafenib and trametinib until toxicity resolves to ≤ Grade 1 or baseline. Reduce dabrafenib and trametinib at the next lower dose per Table 6-7. Re-escalation of the subject's dose is recommended if criteria in Section 6.3.2 are met. 
4th occurrence:
 
 Discontinue PDR001/placebo, dabrafenib and trametinib.
Grade 3: Moist desquamation, ulceration, blistering or severe pain of the hands or feet, or severe discomfort that causes the subject to be unable to work or perform activities of daily living	
 Recommend topical therapy for symptomatic relief 	
1st occurrence:
 
 Interrupt PDR001/placebo, dabrafenib and trametinib until toxicity resolves to ≤ Grade 1 or baseline. Once recovered, reinstate PDR001/placebo, and reduce dabrafenib and trametinib to the next dose level per Table 6-7. Re-escalation of the subject's dose is recommended if criteria in Section 6.3.2 are met. 
2nd occurrence:
 
 Interrupt PDR001/placebo, dabrafenib and trametinib until toxicity recovers to ≤ Grade 1 or baseline. 
 Once recovered, reinstate PDR001/placebo, and reduce dabrafenib and trametinib to the next dose level per Table 6-7. Re-escalation of the subject's dose is recommended if criteria in Section 6.3.2 are met. 
3rd occurrence:
 
 Discontinue PDR001/placebo, dabrafenib and trametinib.

[figure not shown]

6.3.3.10 Mandatory dose modifications and recommended clinical management guidelines for neutropenia and thrombocytopenia

Guidelines for dose modification for neutropenia and thrombocytopenia suspected to be related to study treatment by the investigator are provided in [Table 6-17](#).

[figure not shown]
Table 6-17 Mandatory dose modifications and recommended clinical management guidelines for neutropenia and thrombocytopenia

Neutropenia and thrombocytopenia suspected AEs (NCI-CTCAE v4.03)		
Grade	Recommended adverse event management guidelines	Mandatory dose modification requirements
Neutropenia		
Grade 1, 2	NA	
 Continue PDR001/placebo, dabrafenib and trametinib at the same dose.
Grade 3, 4	
 Monitor blood test more frequently (every 7 days for Grade 3, and 3-5 days for Grade 4). 	
1st occurrence:
 
 Interrupt PDR001/placebo, dabrafenib and trametinib until toxicity recovers to \leq Grade 2 or baseline. 
 Restart PDR001/placebo at the same regimen, and reduce dabrafenib and trametinib at the next dose level. Re-escalation of the subject's dose is recommended if criteria in Section 6.3.2 are met. 
2nd occurrence:
 
 Interrupt PDR001/placebo, dabrafenib and trametinib until toxicity recovers to \leq Grade 2 or baseline. 
 Restart PDR001/placebo at the same regimen, and reduce dabrafenib and trametinib at the next dose level. Re-escalation of the subject's dose is recommended if criteria in Section 6.3.2 are met. AE resolution to \leq Grade 2 or baseline must occur within a maximum period of 12 weeks since Grade 3 or 4 event has been identified, otherwise PDR001/placebo must be permanently discontinued. 
3rd occurrence:
 
 Permanently discontinue PDR001/placebo and interrupt dabrafenib and trametinib until toxicity recovers to \leq Grade 2 or baseline.

Neutropenia and thrombocytopenia suspected AEs (NCI-CTCAE v4.03)

Grade	Recommended adverse event management guidelines	Mandatory dose modification requirements
Febrile Neutropenia	
 Apply Institutional guidelines 	
 Once recovered, reduce dabrafenib and trametinib to the next dose level. Re-escalation of the subject's dose is recommended if criteria in Section 6.3.2 are met. 
4th occurrence:
 
 Permanently discontinue dabrafenib and trametinib 
 Follow modification guide for neutropenia Grade 4 (above).
Thrombocytopenia		
Grade 1, 2, 3 without clinically significant bleeding	
 Grade 3: monitor blood test more frequently (every 7 days) 	
 Continue PDR001/placebo, dabrafenib and trametinib at the same dose.
Grade 3 with clinically significant bleeding Grade 4	
 Grade 3: monitoring blood test more frequently (every 3-5 days) 	
1st occurrence:
 
 Interrupt PDR001/placebo, dabrafenib and trametinib until toxicity resolves to \leq Grade 2 or baseline. 
 Restart PDR001/placebo, dabrafenib and trametinib at same dose. 
2nd occurrence:
 
 Interrupt PDR001/placebo, dabrafenib and trametinib until toxicity resolves to \leq Grade 2 or baseline. 
 Restart dabrafenib and trametinib at the next lower dose per Table 6-7 and restart PDR001/placebo. Re-escalation of the subject's dose is recommended if criteria in Section 6.3.2 are met. AE resolution to \leq Grade 2 or baseline must occur within a maximum period of 12 weeks since Grade 3 with clinically significant bleeding or Grade 4 event has been identified, otherwise PDR001/placebo must be permanently discontinued. 
3rd occurrence:
 
 Interrupt PDR001/placebo, dabrafenib and trametinib until toxicity resolves to \leq Grade 2 or baseline. 
 Restart dabrafenib and trametinib at another lower

Neutropenia and thrombocytopenia suspected AEs (NCI-CTCAE v4.03)

Grade	Recommended adverse event management guidelines	Mandatory dose modification requirements
		dose per Table 6-7 . Re-escalation of the subject's dose is recommended if criteria in Section 6.3.2 are met.
		4th occurrence: 
 • Interrupt PDR001/placebo, dabrafenib and trametinib until toxicity resolves to ≤ Grade 2 or baseline. • Permanently discontinue dabrafenib and trametinib.

6.3.3.11 Mandatory dose modifications and recommended clinical management guidelines for adverse events including abnormal laboratory related AEs

Guidelines for dose modification for adverse events including abnormal laboratory related AEs suspected to be related to study treatment by the investigator are provided in [Table 6-18](#).

Table 6-18 Mandatory dose modifications and recommended clinical management guidelines for adverse events including abnormal laboratory related AEs

Non-Hematologic AEs (except Grade 2 alopecia, Grade 2 fatigue) and abnormal laboratory related AEs (except neutropenia, thrombocytopenia) (NCI-CTCAE v4.03)		
Grade	Recommended adverse event management guidelines	Mandatory dose modification requirements
Grade 1-2 tolerable	
 • Monitor closely. • Provide supportive care according to institutional standards. 	
 • Continue PDR001/placebo, dabrafenib and trametinib at the same dose.

Non-Hematologic AEs (except Grade 2 alopecia, Grade 2 fatigue) and abnormal laboratory related AEs (except neutropenia, thrombocytopenia) (NCI-CTCAE v4.03)

Grade	Recommended adverse event management guidelines	Mandatory dose modification requirements
Grade 2 intolerable or Grade 3	
• Monitor closely• Provide supportive care according to institutional standards	
1st or 2nd occurrence:
 
• Interrupt PDR001/placebo, dabrafenib and trametinib until toxicity recovers to \leq Grade 1 or baseline.• Restart PDR001/placebo, dabrafenib and trametinib at the same dose.• AE resolution to \leq1 Grade or baseline must occur within a maximum period of 12 weeks since intolerable Grade 2 or Grade 3 event has been identified, otherwise PDR001 must be permanently discontinued. 
3rd occurrence:
 
• Permanently discontinue PDR001/placebo. Interrupt dabrafenib and trametinib until toxicity recovers to \leq Grade 1 or baseline.• Restart dabrafenib and trametinib at the next lower dose per Table 6-7. Re-escalation of the subject's dose is recommended if criteria in Section 6.3.2 are met. 
4th occurrence:
 
• Permanently discontinue dabrafenib and trametinib.

Non-Hematologic AEs (except Grade 2 alopecia, Grade 2 fatigue) and abnormal laboratory related AEs (except neutropenia, thrombocytopenia) (NCI-CTCAE v4.03)

Grade	Recommended adverse event management guidelines	Mandatory dose modification requirements
